Brief Description. The Meso Scale Discovery platform will be used with a custom V-PLEX kit to assess levels of multiple cytokines elevated in people with Down syndrome, including four cytokines that will be used to create a composite Cytokine Score: IP10, TNFa, CRP, IL6. A two-sided, paired Student's t-test will be used to determine the significance of any changes in the Cytokine Score observed.

Name. Change in levels of neurotoxic metabolites in the kynurene pathway.

Type. Tertiary Endpoint.

Time Frame. Baseline and 16 weeks.

Brief Description. Using established mass spectrometry protocols, identification and quantification of kynurene, quinolinic acid, and the kynurene/tryptophan ratio will be performed. A two-sided, paired Student's t-test with FDR correction will be used to determine the significance of any changes observed.

Name. Change in levels of autoantibodies related to AITD.

Type. Tertiary Endpoint.

Time Frame. Baseline and 16 weeks.

Brief Description. Levels of autoantibodies associated with hypothyroidism including anti-thyroperoxidase (TPO), anti-thyroglobulin (TG), and anti-thyroid stimulating hormone receptor (TSHr), will be assessed using established clinical assays. A two-sided, paired Student's t-test with FDR correction will be used to determine the significance of any changes observed.

Name. Change in levels of celiac disease-associated autoantibodies.

Type. Tertiary Endpoint.

Time Frame. Baseline and 16 weeks.

Brief Description. Levels of autoantibodies associated celiac disease including anti-tissue transglutaminase (tTG) and anti-deamidated gliadin peptide (DGP), will be assessed using established clinical assays. A two-sided, paired Student's t-test with FDR correction will be used to determine the significance of any changes observed.

Name. Change in Leiter 3 International Performance Scale scores.

Type. Tertiary Endpoint.

Time Frame. Baseline and 16 weeks.

Brief Description. The Leiter 3 cognitive battery provides a broad non-verbal assessment of cognitive function, including executive function and spatial processing. We will employ the Sustained attention, Nonverbal Stroop Tasks, Forward and Backward Memory and Sequential Order subdomains, to assess inhibitory control, cognitive flexibility, working memory, and spatial processing respectively. An FDR-corrected Wilcoxon signed-rank test (matched pairs) will be used to determine the significance of any changes observed.

Name. Change in CANTAB scores.

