Informed consent and assent forms will also be obtained before or at the screening visit. After receiving results from all screening tests and confirming eligibility, a study doctor will prescribe Tofacitinib from the UCHealth or CU Anschutz Medical Center Investigational Pharmacy. We anticipate participants will return for their baseline visit within approximately four weeks of their screening visit. If the duration between Screening and Baseline visit is longer than 4 weeks, study doctors may order screening labs again at their discretion. At the baseline visit, participants will be instructed to begin administration of oral Tofacitinib at 5 mg BID the following morning. Study visits are timed at Time 0 (baseline), 2, 4, 8, 12, and 16-weeks throughout the course of treatment, as well as 2 weeks after ending treatment (18 weeks in total to complete study visits). Participants in the Extension Arm will have an additional visit at 28 weeks with the final follow-up visit at 40-week. Each study visit will occur +/- 3-days of this schedule determined from Time 0 (baseline), except for Extension Arm visits that will occur +/- 7 days of the ideal visit schedule. Missed study visits or visits that occur outside of this window will be reported as a protocol deviation/violation and will not change the original schedule. A missed study visit that was supposed to include dispense of Tofacitinib should be rescheduled, even if outside the allowed window. Study doctors will not continue the Tofacitinib prescription without current safety labs.

Condition	Assessment	Minimum score
Moderate-to-severe atopic dermatitis	Eczema Area and Severity Index (EASI)	≥ 16
Alopecia areata affecting at least 25% of the scalp	Severity of the Alopecia Tool (SALT)	≥ 25
Moderate-to-severe hidradenitis suppurativa	Hidradenitis suppurativa - Physician's Global Assessment (HS-PGA)	≥ 3
Moderate-to-severe Psoriasis	Psoriasis Area and Severity Index (PASI)	≥ 10
Moderate-to-severe Vitiligo	Vitiligo Extent Tensity Index (VETI)	≥ 2

Table 1. Minimum score for inclusion criteria for each skin condition.

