Thyroid Stimulating Hormone (TSH)	11.12.2020	X	N/A	N/A	N/A	*	N/A	X	N/A	X	X

Table 2. Schedule of safety labs. 'X'= Test performed; N/A = Not applicable. % This visit only occurs for participants who ended Tofacitinib treatment at Visit 7. E = Extension arm only visits * Follow-up required only if Screening Visit results are positive or participant is known thyroid dysfunction . ^ For females if not surgically sterile or two years post-menopause.

Visit 7 Considerations for the 16-week Endpoint.

If a participant misses 15% or more of Tofacitinib doses (3 or more pills) in the 7 days before a scheduled Visit 7 for any reason, Visit 7 will be rescheduled to ensure 7 days of compliant study drug intake before this endpoint visit. This may be outside the original +/- 3 days window for Visit 7. Treatment will not be extended beyond 18 weeks before a Visit 7 occurs. This will be recorded as a protocol deviation.

Similarly, if a participant reports a confounding adverse event within 7 days of Visit 7, Visit 7 will be rescheduled so that at least 7 days have passed since the condition was resolved. This may be outside the original +/- 3 days window for Visit 7. Treatment will not be extended beyond 18 weeks before a Visit 7 occurs. This will be recorded as a protocol deviation.

Extension Arm – Study Drug.

Some participants may not respond, or may not achieve a full response, to Tofacitinib by the end of the 16-week trial. Participants who are likely to benefit from an extension of Tofacitinib will be initially identified by the study doctor at their 8-week visit (Visit 5) using the criteria below, but may be identified as a candidate for the extension trial at subsequent visits at the study doctor's discretion if the criteria are met. Additionally,

participants must remain in good health standing and have no study doctor concerns that would preclude study continuation.

1. Alopecia areata (min. initial qualifying SALT score ≥ 25): Participant shows any decrease in their SALT score from the Baseline score, but SALT score is still ≥ 5 at the 8-week appointment.
 - In cases of alopecia totalis, observable improvement in any hair re-growth on the body would constitute a basis for Extension Arm qualification, such as eyelash or eyebrow re-growth.
 - All cases of alopecia areata present for ≥ 5 years by parent or clinician report will be invited to participate in the Extension Arm, even if no improvement decrease in SALT score is noted by 8 weeks.

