At any time during the study, study doctors may request an additional study visit with a participant to address or follow-up on pressing concerns about safety or reported AEs. In this case, a study coordinator will schedule an additional study visit with the participant and their study partner as soon as possible. This visit may include collection of vitals, physical exam and recording of AEs as necessary, as well as any laboratory tests recommended by the study doctor.

Teleresearch Visits.

To facilitate participation for non-local participants, study doctors may perform a teleresearch visit using Epic. These visits may be implemented at the study doctor's discretion in place of regularly scheduled visits and combined with a remote blood draw to obtain safety labs as needed. Creatine kinase is not collected for teleresearch safety labs. Research labs may be drawn remotely and shipped to the Linda Crnic Institute. Additional study drug may be dispensed at study doctor's discretion at a prior visit in anticipation of a scheduled teleresearch visit, or shipped directly to the participant from the Investigational Pharmacy.

Remote Blood Draws.

For standard safety monitoring, it may be more convenient for the participant to have laboratory tests drawn nearer to their home. The study team may arrange for a qualified phlebotomist to visit the home and subsequent clinical analysis at an accredited lab, or for the participant to go to an alternate facility for a blood draw at their discretion. Participants may always choose to have appointments at their regular study site.

COVID-19 vaccinations and boosters.

Participants who receive a COVID-19 vaccination or booster will be advised to stop taking the study drug for 7 days (14 doses) after receiving the vaccination or booster. The original study timeline will not be altered,

unless suspension of the study drug interferes with a study endpoint (see Visit 7 Considerations for the 16-week Endpoint).

Safety and Adverse Event Monitoring.

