All AEs are recorded from the Baseline visit (Visit 2) when the IP begins through the final follow-up visit 2 weeks after the last Tofacitinib dose, or final visit of the Extension Arm. Additionally, AEs that occur at Screening (Visit 1) that are considered to be directly related to the screening procures will be reported. AEs are documented in terms of a medical diagnosis. When this is not possible, the AE is documented in terms of signs and/or symptoms observed by the study doctor or reported by the participant. AEs are recorded in REDCap and printed copies of the completed REDCap forms are kept in the participant’s source documentation file. AE incidence rates (number of events per 100 patient years) for the study as a whole will be calculated for monthly reports (see *Safety and Adverse Event Reporting* below).

In published studies evaluating Tofacitinib for treatment of rheumatoid arthritis, the incidence rate was as follows for various AEs: 9.4 for SAEs, 2.7 for serious infection, 3.9 for herpes zoster (shingles), 0.3 for opportunistic infection not including tuberculosis, 0.2 for tuberculosis, 0.9 for malignancies, and 0.1 for gastrointestinal perforations. These AE rates are anticipated by this study protocol and have already been deemed safe by the FDA via their approval of Tofacitinib for marketing.

When any AE, regardless of classification, is reported by a participant to any study staff, that personnel will immediately relay the AE information to a study doctor, who will classify the AE appropriately and decide if any follow-up actions should be taken. If needed, follow-up appointments will occur in a timely manner as dictated by the nature of the AE and the discretion of the PIs and study doctors. Similarly, all blood chemistry and laboratory monitoring values will be reviewed as soon as they are available by a study doctor to ensure all results are within normal ranges for a person with Down syndrome or for that specific participant. Abnormal findings will be reported as an AE as appropriate. Detailed information about every AE will be incorporated into a Monthly Progress and Safety Report, as well as Annual Reports, as described below.

Finally, any incident, experience, or outcome may be considered an unanticipated problem (UAP) if it meets the following criteria: 1) it is considered “unexpected” as defined above, 2) it is considered possibly or

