10) Participants will be advised to receive all vaccinations, including for COVID-19, before beginning tofacitinib. However, if they are already taking tofacitinib, they may be advised to withhold tofacitinib for a period of time before and/or after receiving a COVID-19 booster, in accordance with American College of Rheumatology (ACR) guidance. Current ACR guidelines recommend holding tofacitinib for 7 days (14 doses) after vaccination. When appropriate amid changing guidelines, study doctors will encourage participants and their study partners to pursue boosters in accordance with best practice guidelines, even if it results in time off tofacitinib during the study period.

COVID-19 Symptoms, Diagnosis, or Exposure.

If at any point in the study period, a participant and/or their study partner is not allowed on campus due to COVID-19 exposure, symptoms, or diagnoses, the workflows detailed in **Figure 7** below will apply, depending on when in the study the COVID-19 event is noted by a study coordinator.

Participants who are diagnosed with COVID-19 will be reminded of their “What to do if I get COVID-19” card and instructed to bring this information to their treating physician. The participant and their physician will decide whether the participant should continue taking Tofacitinib and remain enrolled in the study. In this scenario, study PIs will be available for consultation with the participant’s physician. The study team will not provide any COVID-19 care but will continue to provide Tofacitinib as long as the participant remains enrolled. Study coordinators may make additional medical record requests to capture relevant information about the illness if the participant remains enrolled. Any COVID-19 diagnosis will be recorded as an AE and treated as

[figure not shown]

Figure 7. Flowchart detailing how study coordinators will handle any participant or study partner with COVID-19 symptoms, diagnosis or exposure.

any other infection would be, with study staff following all rules detailed in the *Participant Discontinuation and Trial Stopping* section of the protocol.

V. Description, Risks and Justification of Procedures, and Data Collection Tools

Description of Procedures.

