Method: This number is based on published safety data for Tofacitinib for the treatment of rheumatoid arthritis in the general population, which indicates a rate of 9.4 SAEs per 100 patient years. Given that our trial aims to enroll 47 participants for 16 weeks of treatment (though we anticipate up to seven participants would be lost to attrition at various times during the treatment course) for a maximum total of 14.5 patient years of treatment, a comparable number of SAEs is 1.36.

Specific Aim 2. To determine the impact of JAK inhibition on the immune dysregulation caused by trisomy 21.

The overall goal of our data analysis plan in this Aim is to define which immune processes dysregulated by T21 can be normalized by Tofacitinib treatment, i.e. returned to values observed in typical people. Importantly, data shown in this proposal demonstrate that we have already defined the directionality and average magnitude of the change between people with and without T21. For example, we determined that IFN scores are significantly higher in people with DS (*Figure 3C*) and expect that Tofacitinib will reduce these values. Whereas some of the features dysregulated by T21 may be normalized by Tofacitinib treatment, others may not, and this will provide an important mechanistic insight to understand the molecular underpinnings of immune dysregulation in DS. Accordingly, the endpoints associated with this Specific Aim focus on effects of Tofacitinib (16 weeks of treatment) on four classes of molecular markers of immune dysregulation:

Primary Endpoint: Change in IFN scores in the transcriptome of white blood cells.

Endpoint Definition: Statistically significant reduction in average IFN scores between baseline and 16 weeks as defined by a two-sided, paired Student's t-test.

Method: To determine the impact of Tofacitinib on IFN scores, a two-sided, paired Student's t-test will be used to compare baseline and 16 weeks of treatment for participants with good compliance with the study drug (2 or fewer missed pills) and without a confounding reported adverse event in the 7 days prior to the Visit 7 endpoint. With 40 participants, we have 80% power to detect an effect size of 0.45 with a p-value <0.05, as calculated by G*Power software.

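### The 7-day confounding-event rule protects only the Visit 7 draw and not Baseline, and vaccination is advised before the first dose with no minimum gap to the Baseline draw

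*Combined protocol and SAP*

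**What the plan says.** **Vaccination.** Section IV.D, Precautionary and Informative Measures, item 10: "Participants will be advised to receive all vaccinations, including for COVID-19, before beginning tofacitinib". Section IV.C, Study Visits and Activities, places the first dose just after Baseline, when "participants will be instructed to begin administration of oral Tofacitinib at 5 mg BID the following morning". The exclusion criteria set an interval only for live vaccines (six weeks before inclusion). For participants already on drug, Section IV.C, COVID-19 vaccinations and boosters, says that they "will be advised to stop taking the study drug for 7 days (14 doses) after receiving the vaccination or booster" and refers to the Visit 7 rules if the hold interferes with an endpoint.

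**Safeguards at Visit 7.** Section IV.C, Visit 7 Considerations, has two rules. For 3 or more missed pills in the preceding week, "Visit 7 will be rescheduled to ensure 7 days of compliant study drug intake before this endpoint visit". For events, "if a participant reports a confounding adverse event within 7 days of Visit 7, Visit 7 will be rescheduled", to at least 7 days after resolution. Section VII, Specific Aim 2, then limits the IFN score, Cytokine Score and kynurenine tests to participants with good compliance and "without a confounding reported adverse event in the 7 days prior to the Visit 7 endpoint".

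**Baseline.** Neither event rule has a Baseline counterpart. Under Safety and Adverse Event Monitoring, "All AEs are recorded from the Baseline visit (Visit 2) when the IP begins"; the only earlier events reported are those directly related to screening procedures.

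**Endpoints.** The IFN score (primary) and the Cytokine Score, built from "four cytokines that will be used to create a composite Cytokine Score: IP10, TNFa, CRP, IL6", are compared between Baseline and 16 weeks by a two-sided paired t-test. Success is a significant reduction.

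**The concern.** Every participant receives tofacitinib, so the Baseline value is the only comparator. If a marker is temporarily raised at the Baseline draw and has settled by week 16, the paired difference records a fall that the drug did not cause. The mirror-image case, a temporary rise at Visit 7, would push the other way, but that is the case the plan reschedules or filters out when an event is reported. Removing disturbances at one end only leaves a net tilt toward success, on a primary endpoint among others.

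The protocol accepts the underlying premise. It treats recent adverse events as confounders of these analyses, and Section IV.D, item 9, names SARS-CoV-2 infection as a possible confounder or covariate. Item 10 matters because it directs a foreseeable immune stimulus to the side of the comparison that has no event rule.

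**Working it through.** **1. The plan's own figure.** Section VII gives 80% power for n = 40, effect size 0.45 and two-sided 0.05. The exact paired t calculation (39 df, noncentrality 0.45 × √40 = 2.846) gives 79.3%, and the effect with exactly 80% power is 0.454. The stated figure reproduces and is not in dispute.

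**2. The two draws side by side.**

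| Disturbance shortly before the draw | Baseline | Visit 7 |
|---|---|---|
| Confounding adverse event within 7 days | No rule; generally not recorded | Visit moved; participant filtered from the tests |
| COVID-19 vaccine | No interval | 7-day hold, which can trigger the missed-dose rule |
| Other non-live vaccine, no reported event | No rule | No rule |
| Live vaccine | Excluded within six weeks of inclusion | Excluded if planned during the study |
| Persistent COVID-19-like symptoms | Visit rescheduled | Visit rescheduled |

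The first two rows are asymmetric; the others are broadly alike.

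**3. What the COVID-19 hold does at Visit 7.** Suppose vaccination falls k days before Visit 7 and exactly 14 twice-daily doses are then held. Doses missed in the last 7 days are 2k for k ≤ 7 and 28 − 2k for k = 8 to 14. Three or more are missed for k = 2 to 12, so the visit moves. It can stand again when 28 − 2k ≤ 2, that is k ≥ 13 days. For k = 0 or 1 (0 or 2 doses missed), only a reported confounding event moves the visit.

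**4. Size under assumptions.** The documents do not give the number m of the 40 analysed participants with a recent disturbance at Baseline, or its height D in SDs of the paired difference. Both are assumed here. With no drug effect:

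spurious mean reduction = (m/40) × D

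For example, 4/40 × 1 = 0.10 SD, which is 0.10/0.45 = 22% of the planned detectable effect. Simulated chance of a significant reduction (40 independent normal differences, m of them shifted by D, two-sided 0.05, reductions counted; nominal 2.5%):

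| m of 40 | D = 0.5 | D = 1 | D = 2 |
|---|---|---|---|
| 1 | 2.9% | 3.4% | 4.1% |
| 2 | 3.5% | 4.5% | 6.4% |
| 4 | 4.7% | 7.6% | 14.7% |

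If 2 other participants have the same rise at Visit 7 (m = 4, D = 1), the net shift is (4 − 2)/40 × 1 = 0.05 SD and the chance falls from 7.6% to 3.6%. If D = 0 there is no inflation.

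**The case against.** **Vaccine effect.** A reader might infer that the vaccination advice does bias the scores. The documents do not support that. No section says that vaccination raises the IFN score or Cytokine Score, by how much, or for how long; item 9 concerns infection, not vaccination. This objection stands: the point is a risk of unknown size.

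**Timing.** A reader might also infer that the plan pushes vaccines into a run-in just before Baseline. There is no run-in, and item 10 sets no window, so vaccination months before screening complies equally. Under Combined Screening and Baseline Activities, the Screening draw serves as Baseline when the drug can start within five days, and vaccination may then follow the draw. These limits also stand.

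**Visit 7.** It would be wrong to read the hold as a vaccine washout. It serves drug exposure, which has no Baseline analogue. It covers COVID-19 vaccines only, and the 13-day figure depends on exactly 14 doses being held afterwards, whereas item 10 lets the hold vary. Other non-live vaccines without a reported event are uncovered at both draws and could offset each other.

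**Existing Baseline protection.** The exclusion criteria cover clinically significant active viral infection, recent skin infection and recent antimicrobials, and Section IV.D, item 3, moves any visit for persistent COVID-19-like symptoms. Table 3 schedules CRP and ESR at Screening and Baseline, so an acute-phase rise between two separate draws could be seen. This protection is real but partial, and no rule ties a CRP or ESR rise to deferral or to the analysis set.

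None of this removes the core: the 7-day event rule and filter are one-sided, whether or not vaccines matter.

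**Conclusion.** The concern holds as a one-sided safeguard that risks bias toward an apparent reduction in the IFN score, Cytokine Score and kynurenine analyses. The direction follows from the design, provided that the disturbance raises the marker and has settled by week 16. The size cannot be derived from the documents. At the lower assumed inputs the inflation is slight (2.9% to 4.5% against 2.5%). Reaching 14.7% takes four affected participants, each raised by 2 SD, with no offset at Visit 7, and nothing in the documents indicates that this is likely. The stronger conclusion, that the advice invalidates the primary endpoint, is not supported. This is a low-severity improvement, worth making because it is cheap and closes off an alternative explanation that a single-arm trial cannot otherwise rule out.

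**What to change.** 1. **Apply the existing rule at both ends.** In the Visit 7 Considerations, extend the 7-day confounding-event rescheduling rule to the Baseline research draw, or to the Screening draw when it serves as Baseline. In Section VII, Specific Aim 2, require no confounding event in the 7 days before either draw for the IFN score, Cytokine Score and kynurenine tests.
2. **Record what the rule needs.** Collect vaccination dates and intercurrent events for the 14 days before Baseline and before Visit 7. Add to item 10 that, where feasible, the Baseline draw should fall at least 14 days after a non-live vaccine. The advice to vaccinate stays. This is needed because a symptomless vaccination would not trigger the event rule.
3. **Add one sensitivity analysis.** Exclude participants vaccinated within 14 days before either draw. For those vaccinated before Baseline, the Screening research sample could be used instead where it is separate and predates the vaccination. It is not available as a substitute after a combined visit.

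**Cost.** A few participants may wait up to about two weeks. That is not free: they have moderate-to-severe disease, other immunosuppressants are barred, and some travel from out of state. The visit schedule already tolerates more than four weeks between Screening and Baseline, with repeat labs at the study doctor's discretion. Using Screening samples adds RNA-seq and cytokine assays for flagged participants only. If 4 of 40 were excluded instead, the effect detectable with 80% power would rise from 0.454 to about 0.454 × √(40/36) = 0.48.
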